7.2.3. Vital Signs

Vital sign measurements (including oxygen saturation, oral temperature, respiratory rate, and supine BP, and pulse rate) will be obtained at the timepoints specified in [Appendix 4](#).

Blood pressure and pulse rate measurements should be performed using the same arm for each reading and measurements should be taken after the subject has been resting in the supine position for at least 5 minutes.

When vital sign measurements are scheduled at the same time as blood draws, the blood draws will be obtained at the scheduled timepoint, and the vital sign measurements will be obtained prior to and as close as possible to the scheduled blood draw.

7.2.4. 12-lead Electrocardiogram

A 12-lead ECG (including PR, RR, QRS, and QT interval parameters) will be obtained after the subject has been resting for at least 10 minutes in the supine position at the timepoints specified in [Appendix 4](#). The QT interval will be corrected for heart rate by Fridericia's ($QTcF = QT/[RR]^{1/3}$) formula.

When 12-lead ECGs are scheduled at the same time as blood draws, the blood draws will be obtained at the scheduled timepoint, and the 12-lead ECGs will be obtained prior to and as close as possible to the scheduled blood draw.

7.2.5. Physical Examination

A complete or abbreviated physical examination will be performed at the timepoints specified in [Appendix 4](#). Complete physical examinations will evaluate general appearance and the following body systems/organs: dermatological; head and eyes; ears, nose, mouth, and throat; pulmonary; cardiovascular; abdominal; lymphatic; musculoskeletal/extremities; and neurological. Weight and height will be reported (height only reported during Screening). Abbreviated physical examinations will evaluate general appearance and the following body systems/organs: dermatological; pulmonary; cardiovascular; abdominal; and neurological.

8. SAMPLE SIZE AND DATA ANALYSIS

8.1. Determination of Sample Size

This study is planned to enroll up to 24 healthy adult male and female subjects (women of non-childbearing potential only). Six subjects will participate in each cohort.

Replacement subjects may be enrolled only if deemed necessary by the Sponsor.

Every attempt will be made to enroll at least 1 subject of each sex in each cohort.

No formal statistical assessment of sample size has been conducted. The sample size chosen for this study is common in single-ascending dose studies and is considered sufficient to achieve the objectives of the study.

8.2. Analysis Populations

8.2.1. Study Populations

The **PK population** will consist of all subjects who received at least 1 dose of LOXO-305, have at least 1 quantifiable PK concentration, and for whom at least 1 PK parameter can be computed. A subject may be excluded from the PK summary statistics and statistical analysis if the subject has an AE of vomiting that occurs at or before 2 times the median t_{max} . The impact of protocol deviations on the PK population will be evaluated case-by-case basis.

The **safety population** will consist of all subjects who received 1 dose of LOXO-305. Subjects will be classified into groups based on actual treatment received.

8.3. Pharmacokinetic Analysis

Serial PK blood samples for the analysis of plasma concentrations of LOXO-305 will be collected from predose through 168 hours post-LOXO-305 dose for Treatments A, B, and C.

Whenever possible, the following PK parameters will be calculated for each subject, based on the plasma concentrations of LOXO-305 (as appropriate):

AUC_{0-24} area under the concentration-time curve from hour 0 to 24 hours postdose, as calculated by the linear trapezoidal method

AUC_{0-t} area under the concentration-time curve (AUC) from hour 0 to the last measurable concentration, calculated using the linear trapezoidal rule for increasing and decreasing concentrations

AUC_{0-inf} AUC from time 0 extrapolated to infinity, calculated using the formula:

$$AUC_{0-inf} = AUC_{0-t} + \frac{C_t}{\lambda_z}$$

where C_t is the last measurable concentration and λ_z is the apparent terminal elimination rate constant

$\%AUC_{extrap}$ percentage extrapolation for AUC_{0-inf}

C_{max} maximum observed plasma concentration

t_{max} time to maximum observed plasma concentration

λ_z	apparent terminal elimination rate constant, where λ_z is the magnitude of the slope of the linear regression of the log concentration versus time profile during the terminal phase
CL/F	apparent systemic clearance
$t_{1/2}$	apparent plasma terminal elimination half-life (whenever possible), where $t_{1/2} = \ln(2)/\lambda_z$
V_z/F	apparent volume of distribution at terminal phase

Pharmacokinetic calculations will be performed using commercial software such as Phoenix™ WinNonlin® Version 8.1 or higher (Certara USA Inc.).

The λ_z and $t_{1/2}$ will be calculated by linear least squares regression analysis using the maximum number of points in the terminal log linear phase (eg, 3 or more non-zero plasma concentrations). Other parameters may be added as appropriate. Final PK parameters reported will be detailed in the Statistical Analysis Plan (SAP).

Pharmacokinetic analysis will use actual times as recorded on the eCRF. All statistical analysis will be performed using SAS® Version 9.4 or greater. More details on the analyses will be included in the SAP.

8.3.1. Descriptive Analysis

Plasma concentrations and PK parameters will be summarized with descriptive statistics (number, arithmetic mean, standard deviation, coefficient of variation [CV%], geometric mean, geometric CV%, median, minimum, and maximum).

Individual and mean plasma concentration-time curves (both linear and log linear) will be included in the final report.

8.3.2. Statistical Methodology

Pharmacokinetic dose proportionality will be assessed for Cohorts 1, 2, and 3. Natural log-transformed AUC_{0-24} , AUC_{0-t} , $AUC_{0-\infty}$, and C_{max} of LOXO-305 will be evaluated using a power model of the form:

$$\ln(\text{parameter}) = \text{intercept} + \text{slope} \times \ln(\text{dose}) + \text{random error}$$

For each PK parameter separately, a pooled estimate (across all doses) of slope, corresponding 95% confidence interval, and between-subject CV% will be calculated.

8.4. Safety Analysis

All safety assessments, including AEs and SAEs, vital sign measurements, clinical laboratory evaluations, physical examination results, concomitant medications, and 12-lead ECGs, will be tabulated and summarized where possible, using descriptive methodology, as needed, by timepoint. Unless otherwise specified, baseline value is defined as the last non-missing measurement before administration of LOXO-305. No formal statistical analyses are planned for the safety data. All safety data will be listed by subject.

Concomitant medications will be coded using the WHO Drug Dictionary (WHO Drug Global B3, September 2019) and AEs will be coded using MedDRA Version 22.1 (or higher). The incidence of AEs will be presented by severity and by relationship to study drug as determined by the Investigator ([or designee], [Appendix 1](#) for AE reporting). All TEAEs will be summarized by system organ class and preferred term.

8.5. Data Handling and Record Keeping

Any changes to information in the trial progress notes and other source documents will be initialed and dated on the day the change is made by a CRU staff member authorized to make the change. Changes will be made by striking a single line through erroneous data and clearly entering the correct data (eg, ~~wrong data~~ right data). If the reason for the change is not apparent, a brief explanation for the change will be written adjacent to the change by the clinician.

The Data Management Plan will be approved by the Sponsor.

Data will be validated during data entry by the CRU and verified by the Study Monitor. Data will then be reviewed by the data management group to resolve any outstanding issues. Listings will be generated after the database is cleaned by data management and will be reviewed by the Covance scientific team. The eCRF and ancillary data will be converted into final SAS® datasets following Study Data Tabulation Model or client-provided specifications. The final datasets structure will be verified using Web Submission Data Manager®, while the dataset content will be peer reviewed by an independent programmer.

The tables, figures, and listings (TFLs) will be programmed per the final SAP. All TFLs will be peer reviewed by an independent programmer. In addition, draft TFLs will be reviewed by the Covance scientific team during the dry run and data review meetings.

The peer review will be performed by independent programmers following the quality control process and programming checklists.

8.6. Quality Control and Quality Assurance

Quality control and quality assurance will be performed according to Covance standard operating procedures or per client request, and as applicable, according to the contract between Covance and the Sponsor.

9. ADMINISTRATIVE ASPECTS

9.1. Change in Protocol

There will be no alterations in the protocol without agreement between the Sponsor and the Investigator (or designee).

There will be no alterations in the protocol affecting subject safety without the express written approval of the Sponsor, Investigator (or designee), and the IRB (see Form FDA 1572).

9.2. Site Initiation Visit/Investigator Meeting

Prior to the start of the clinical study, the representative(s) of the Sponsor will meet with the Investigator (or designee) and appropriate CRU staff to familiarize the Investigator (or designee) and CRU staff with the materials necessary for conducting the clinical study.

9.3. Disclosure

All information provided regarding the study, as well as all information collected/documenting during the study, will be regarded as confidential. The Investigator (or designee) agrees not to disclose such information in any way without prior written permission from the Sponsor.

Any publication of the results, in part or in total (eg, articles in journals or newspapers, oral presentations, abstracts) by the Investigator (or designee) or their representative(s), shall require prior notification and review, within a reasonable timeframe, by the Sponsor, and cannot be made in violation of the Sponsor's confidentiality restrictions or to the detriment of the Sponsor's intellectual property rights.

9.4. Monitoring

The Sponsor will designate a Study Monitor who will be responsible for monitoring this clinical trial. The Sponsor's Study Monitor will monitor the study conduct, proper eCRF and source documentation completion and retention, and accurate study drug accountability. To this end, the Sponsor's Study Monitor will visit the CRU at suitable intervals and be in frequent contact through verbal and written communication. It is essential that the Sponsor's Study Monitor has access to all documents (related to the study and the individual participants) at any time these are requested. In turn, the Sponsor's Study Monitor will adhere to all requirements for subject confidentiality as outlined in the ICF. The Investigator (or designee) and Investigator's staff will be expected to cooperate with the Sponsor's Study Monitor, to be available during a portion of the monitoring visit to answer questions, and to provide any missing information.

9.5. Institutional Review Board

In accordance with US Title 21 Code of Federal Regulations (CFR) 56, the protocol, advertisement, ICF, and other information provided to subjects will be reviewed and approved by the IRB. The Sponsor will supply relevant material for the Investigator (or designee) to submit to the IRB for the protocol's review and approval. Verification of the

IRB unconditional approval of the protocol and the written ICF statement will be transmitted to the Investigator (or designee).

The IRB will be informed by the Investigator (or designee) of subsequent protocol amendments and of serious and unexpected AEs. Approval for protocol amendments will be transmitted in writing to the Investigator (or designee). If requested, the Investigator (or designee) will permit audits by the IRB and regulatory inspections by providing direct access to source data/documents.

The Investigator (or designee) will provide the IRB with progress reports at appropriate intervals (not to exceed 1 year) and a Study Progress Report following the completion, termination, or discontinuation of the Investigator's (or designee's) participation in the study.

9.6. Informed Consent

Written informed consent for the study will be obtained from all subjects before protocol-specific procedures are carried out. The ICF will be approved (along with the protocol) by the IRB and will be acceptable to the Sponsor.

The Investigator (or designee) will explain the nature of the study and the action of the test product. The subjects will be informed that participation is voluntary and that they can withdraw from the study at any time. In accordance with 21 CFR 50, the informed consent process shall be documented by the use of a written ICF approved by the IRB and signed by the subject prior to protocol-specific procedures being performed.

The subject will sign 2 copies of the ICF. One copy will be given to the subject, and the other will be maintained with the subject's records.

9.7. Records

The results from data collected at Screening and during the study will be recorded in the subject's eCRF. To maintain confidentiality, the subjects will be identified only by numbers.

The completed eCRFs will be transferred to the Sponsor (or designee). Copies of each eCRF will be retained by the Investigator (or designee). All source documents, records, and reports will be retained by the CRU in accordance with 21 CFR 312.62(c).

All primary data, or copies thereof (eg, laboratory records, eCRFs, data sheets, correspondence, photographs, and computer records), which are a result of the original observations and activities of the study and are necessary for the reconstruction and evaluation of any study report, will be retained in the CRU archives.

9.8. Reference to Declaration of Helsinki/Basic Principles

The study procedures outlined in this protocol will be conducted in accordance with the US CFR governing Protection of Human Subjects (21 CFR 50), Financial Disclosure by Clinical Investigators (21 CFR 54), IRBs (21 CFR 56), Investigational New Drug Application (21 CFR 312), Applications for FDA Approval to Market a New Drug (21 CFR 314), and Radioactive Drugs for Certain Research Uses (21 CFR 361.1), as appropriate. As such, these

sections of US Title 21 CFR, along with the applicable ICH Guidelines, are commonly known as Good Clinical Practices, which are consistent with the Declaration of Helsinki.

9.9. Financing and Insurance

Financing and insurance will be addressed in a separate agreement.

11. APPENDICES

Appendix 1: Adverse Event Reporting

Adverse Events

Definition of Adverse Events

An adverse event (AE; or adverse experience) is defined as any untoward medical occurrence experienced by a patient or healthy adult subject, whether or not considered drug-related by the Investigator (or designee). A treatment-emergent adverse event (TEAE) is an AE that starts on or after the first administration of study drug.

The following are all AEs:

- unfavorable changes in general condition;
- subjective or objective signs/symptoms;
- concomitant diseases or accidents;
- clinically relevant adverse changes in laboratory parameters observed in a subject during a clinical study.

Adverse events comprise all disturbances of general health status, subjective and objective disease symptoms (including laboratory abnormalities that are deemed clinically significant by the Investigator [or designee]), and accidents observed in the context of a clinical trial, irrespective of a possible causal relationship with the administration of the trial substance.

Categorization of Adverse Events

The severity of AEs will be categorized based on the National Cancer Institute CTCAE Version 5.0 as follows:

- **Grade 1 Mild:** Asymptomatic or mild symptoms; clinical or diagnostic observations only; intervention not indicated
- **Grade 2 Moderate:** Minimal, local or noninvasive intervention indicated; limiting age-appropriate instrumental Activities of Daily Living (ADL)*
- **Grade 3 Severe or medically significant but not immediately life-threatening:** Hospitalization or prolongation of hospitalization indicated; disabling; limiting self-care ADL**
- **Grade 4 Life-threatening consequences:** An event that puts the subject at immediate risk of death
- **Grade 5:** Death related to AE.

Note: Not all grades are appropriate for all AEs. Therefore, some AEs are listed within the CTCAE with fewer than 5 options for grade selection. Grade 5 (death) is not appropriate for some AEs and therefore is not an option.

* Instrumental ADL refer to preparing meals, shopping for groceries or clothes, using the telephone, managing money, etc.

**Self-care ADL refer to bathing, dressing and undressing, feeding self, using the toilet, taking medications, and not bedridden.

The Investigator (or designee) will make a determination of the relationship of the AE to the study drug using a 2-category system according to the following guidelines:

- **NOT RELATED** = The time course between the administration of investigational product and the occurrence or worsening of the AE rules out a causal relationship and another cause (eg, concomitant drugs, therapies, complications, comorbidities) is suspected.
- **RELATED** = The time course between administration of investigational product and the occurrence or worsening of the AE is consistent with a causal relationship and no other cause (eg, concomitant drugs, therapies, complications, comorbidities) can be identified.

An AE is associated with the use of the drug if there is a reasonable possibility that the experience may have been caused by the drug.

Pregnancy

As information is available, a pregnancy (including pregnancy in female partners of male subjects) diagnosed through End of Study (EOS) or Early Termination (ET; if the subject discontinues from the study and does not complete a follow-up phone call) and for up to 90 days after study drug administration should be reported by the Investigator (or designee) via email to Covance or the Sponsor's Clinical Safety Representative within 24 hours of being notified. Covance or the Sponsor's Clinical Safety Representative will then forward the Pregnancy Form to the Investigator (or designee) for completion.

email: [contact]

A subject becoming pregnant while on study drug will immediately be withdrawn from the study and ET study procedures will be performed. The subject or partner should be followed by the Investigator (or designee) until completion of the pregnancy. If the pregnancy ends for any reason before the anticipated date, the Investigator (or designee) should notify Covance or the Sponsor's Clinical Safety Representative. At the completion of the pregnancy, the Investigator (or designee) will document the outcome of the pregnancy. If the outcome of the pregnancy meets the criteria for immediate classification as an SAE (ie, postpartum complication, spontaneous abortion, stillbirth, neonatal death, or congenital anomaly), the Investigator (or designee) should follow the procedures for reporting an SAE.

Male subjects will be instructed to notify the Investigator immediately if they discover their sexual partner is pregnant. In this instance, the partner must provide written consent before pregnancy information can be collected. When a CRU becomes aware that the female partner of a male subject is pregnant, they are to contact the Investigator (or designee) immediately (within 24 hours of the CRU staff becoming aware of the event) in addition to notifying Covance or the Sponsor's Clinical Safety Representative via email.

All pregnancies should be recorded on the AE eCRF (as appropriate), in addition to completion of the required pregnancy forms. If the Investigator (or designee) suspects that a pregnancy was the result of an interaction between the study treatment and the contraceptive method, in addition to the pregnancy the drug interaction should also be captured as a separate AE.

Definition of Serious Adverse Events

An SAE (by FDA definition) is any adverse drug experience occurring at any dose that results in any of the following outcomes:

- Death;
- A life-threatening adverse drug experience (ie, one that places the subject, in the view of the Investigator [or designee], at immediate risk of death);
- Inpatient hospitalization or prolongation of existing hospitalization;
- A persistent or significant disability/incapacity;
- A congenital anomaly/birth defect;
- An important medical event that may require medical or surgical intervention to prevent 1 of the above outcomes.

Important medical events that may not result in death, be life-threatening, or require hospitalization may be considered SAEs when, based on appropriate medical judgment, they may jeopardize the patient or subject and may require medical or surgical intervention to prevent 1 of the outcomes listed in this definition.

Unexpected Adverse Drug Reaction

An AE or suspected adverse drug reaction is considered ‘unexpected’ if the event is not listed in the Reference Safety Information section of the Investigator’s Brochure or if it is not listed at the specificity or severity that has been observed for an unapproved investigational medicinal product.

Reporting

The FDA-reportable AEs are AEs that are associated with the use of the drug and represent events that are assessed as serious, related, and unexpected. The FDA-reportable AEs will be reported by the CRU to the Sponsor and the responsible Institutional Review Board. Final determination of whether an event represents a suspected unexpected serious adverse reaction will be the responsibility of the Sponsor.

Within 24 hours of when an AE that is potentially FDA-reportable is first recognized or reported, and within 24 hours of any SAE (regardless of whether the event is assessed as related or unrelated to study drug) being first recognized or reported, Covance or the Sponsor’s Clinical Safety Representative will be notified by the Investigator (or designee) in writing using the following email address:

email: [contact]

To report the SAE, the completed report form should be sent by email to Covance or the Sponsor’s Clinical Safety Representative within 24 hours of awareness. Incoming reports are reviewed during normal business hours. Additional reporting instructions and the SAE Report Form are provided in the Study Manual.

The IRB will be notified of any FDA-reportable AE within the timeframe required by the IRB. The IRB Serious and Unexpected Adverse Experience Submission Form will be completed and submitted with the copy of the written confirmation or summary of the AE.

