5.5. Dose Escalation Criteria and Stopping Rules

Dose escalation to the next dose level (ie, next cohort) will not take place until the Investigator (or designee) and the Sponsor have determined that adequate safety and tolerability data (ie, physical examinations, ECGs, vital sign measurements, clinical laboratory evaluations, and AEs through 168 hours [Day 8] following dosing on Day 1) from the previous, lower dose, cohort has been demonstrated to permit proceeding to the next cohort. A sufficient period of time will be allowed between dosing (168 hours [Day 8], following dosing on Day 1) of the prior cohort and the dosing of the next cohort in order for the Investigator (or Designee) and the Sponsor to adequately review the safety and tolerability data from the prior cohort. Pharmacokinetic data through at least 72 hours (approximately 3 half-lives) will be reviewed to guide dose-escalation decisions or for selection of an alternate dose for evaluation, and/or to confirm the sampling schedule. Data from a minimum of 4 subjects will be reviewed in order to make a dose escalation decision.

The Investigator (or designee) and the Sponsor will make 1 of the following determinations:

1. To continue with the study as planned.

2. To continue with the study and add additional safety evaluations to subsequent cohorts.
3. In the event of the following occurrence:
 - a. One subject at a given dose level experiences a drug-related Common Terminology Criteria for Adverse Events (CTCAE) grade ≥ 3 toxicity (which is not an SAE), which is deemed clinically significant by the Investigator (or designee), with agreement from the Sponsor, a decision will be made as follows:
 - o Adjust to an intermediate dose between the current dose and the next planned dose;
 - o Adjust to an intermediate dose between the current dose and the previous lower dose;
 - o Dose administration may be permitted to continue as deemed by the Investigator (or designee), with agreement from the Sponsor, where the safety parameter assessed does not pose a subject safety risk based on safety knowledge from prior LOXO-305 studies.
 - b. Two or more subjects in a dose level experience a drug-related CTCAE grade ≥ 3 toxicity (which is not an SAE), which are deemed clinically significant by the Investigator (or designee), with agreement from the Sponsor, a decision will be made as follows:

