7.2.1. Adverse Events

Adverse event definitions; assignment of severity, causality, action taken, and outcome; and procedures for reporting SAEs are detailed in [Appendix 1](#).

Subjects will be asked a non-leading HDYF? question such as “Have there been any changes in your health status since Screening/since you were last asked?” at the timepoints specified in [Appendix 4](#) (ie, at Screening [after the ICF is signed], at Check-in [Day -1], at each postdose vital sign measurement, and at an appropriate time for all other days). Subjects will also be encouraged to voluntarily report AEs occurring at any other time through the EOS.

Adverse events, whether volunteered, identified by the subject's responses to HDYF? inquiries, or noted on physical examination, ECG, vital sign measurements, or clinical laboratory evaluations, will be recorded throughout the study (ie, from signing of the ICF until EOS [or ET if the subject discontinues from the study and does not complete a follow-up phone call]), either as subject medical history (if the event is reported as beginning prior to signing of the ICF or if the event occurs prior to study drug administration on Day 1 and is assessed as not related to study procedures by the Investigator [or designee]) or as AEs (if the event occurs after signing of the ICF but prior to study drug administration on Day 1 and is assessed as related to study procedures by the Investigator [or designee], or if the event occurs after study drug administration on Day 1 through EOT or ET regardless of relationship to study drug). From EOT or ET through EOS, only AEs assessed as related to study drug by the Investigator (or designee) are to be reported. All SAEs that develop from the time of ICF signing until EOS (or ET, if the subject discontinues from the study and does not complete a follow-up phone call) are to be reported.

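### Appendix 1's RELATED and NOT RELATED are not complements, so an adverse event with plausible timing and an identified alternative cause fits neither code

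*Protocol*

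**What the plan says.** Protocol Appendix 1 (Categorization of Adverse Events) has the Investigator judge the relationship of each AE to study drug "using a 2-category system according to the following guidelines". For RELATED, the time course "is consistent with a causal relationship and no other cause (eg, concomitant drugs, therapies, complications, comorbidities) can be identified". For NOT RELATED, it "rules out a causal relationship and another cause (eg, concomitant drugs, therapies, complications, comorbidities) is suspected". A separate sentence then says that an AE is associated with use of the drug "if there is a reasonable possibility that the experience may have been caused by the drug".

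The code, or the term drug-related, is used in these places:

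- **Protocol Section 5.5.** Rule 3a begins "One subject at a given dose level experiences a drug-related Common Terminology Criteria for Adverse Events (CTCAE) grade" 3 or higher, and rule 3b begins "Two or more subjects in a dose level experience a drug-related CTCAE grade" 3 or higher. Both are limited to events that are not serious adverse events (SAEs).
- **Protocol Section 7.2.1**, repeated in Section 3.1 and in Appendix 4 footnote j: "From EOT or ET through EOS, only AEs assessed as related to study drug by the Investigator (or designee) are to be reported". SAEs are reported regardless.
- **SAP Section 8.6.1.** A treatment-related treatment-emergent adverse event (TEAE) is one that the Investigator coded as related. A missing code is counted as related.

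**The concern.** Each definition joins two conditions with *and*, and neither is the other's negation. An event whose timing fits the drug, but for which another cause has been identified, fails RELATED on cause and fails NOT RELATED on timing. The Investigator must still choose, and two assessors can choose differently. One who follows the RELATED wording strictly will withhold that code even if the drug is a reasonable explanation.

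Such events are plausible here. Protocol Section 1.5 reports headache, nausea and vomiting after LOXO-305 in a healthy volunteer. In this study subjects fast for at least 10 hours before and 4 hours after dosing, swallow up to 9 capsules, stop caffeine 72 hours before Check-in and have repeated blood draws. A post-dose headache could have both consistent timing and an identifiable competing cause.

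The study is open-label and has no control group, and safety is its primary objective. The Investigator's code is therefore the main formal attribution of events to the drug.

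**Working it through.** The plan gives no figure on this point, so there is none to reproduce. The check is a truth table, followed by a trace of where the code is used.

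**1. Coverage of the two definitions.** RELATED fails only if another cause can be *identified*, whereas NOT RELATED needs one only to be *suspected*. The two words must be kept apart, which gives 2 timing states × 3 cause states = 6 cells.

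| Timing | No other cause suspected | Suspected, not identified | Identified |
|---|---|---|---|
| Consistent with drug | RELATED | RELATED | **neither** |
| Rules out drug | **neither** | NOT RELATED | NOT RELATED |

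Four cells are covered, two meet neither definition, and none meets both. The lower-left cell is harmless, because an assessor who thinks timing rules out the drug will code NOT RELATED anyway. The upper-right cell is the one that matters. (If timing can also be neither consistent nor ruled out, three more cells meet neither definition; the point does not rest on them.)

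**2. Does other text close the gap?**

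- The reasonable-possibility sentence defines a different term, *associated with the use of the drug*. The Reporting part of Appendix 1 lists that term alongside related: "AEs that are associated with the use of the drug and represent events that are assessed as serious, related, and unexpected". The document treats them as separate conditions.
- The SAP's default to related applies to a missing code. An event coded NOT RELATED is not missing.

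**3. Where the code has an effect.**

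| Use | Depends on the code? |
|---|---|
| AE collection from dosing to EOT/ET (Protocol 3.1) | No |
| 24-hour SAE notification (Appendix 1) | No |
| All-AE listings and all-TEAE tables (SAP 8.6.1) | No |
| Non-serious AEs from EOT/ET to EOS (Protocol 7.2.1; Appendix 4 footnote j) | Yes, the only filter |
| Treatment-related TEAE tables (SAP 8.6.1) | Yes, directly |
| Rules 3a and 3b (Protocol 5.5) | Formally yes, but see below |
| Extended follow-up of ongoing AEs (Protocol 4.6, 7.2.1) | Yes, but only permissive |

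Rules 3a and 3b also require clinical significance in the Investigator's judgement, with Sponsor agreement, and both allow dosing to continue. Their other actions are available without the code. Protocol Section 3.1 sets later doses as maxima and allows a repeat or interim cohort. Section 4.6 allows the study to be stopped for AEs with no relatedness condition. Section 5.5 bases escalation on all AEs through 168 hours.

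**4. The late window.** The follow-up call comes 7 ± 2 days after EOT or ET. For completers that is Day 8 + 5 = Day 13 to Day 8 + 9 = Day 17. The half-life is about 20 h (Protocol 1.3.2, a patient estimate with an imputed 24-hour sample) or 24 h (Protocol 3.1, which treats 72 h as about three half-lives). The fraction remaining at time t is 2^(−t/half-life):

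- Completers at 168 h: 2^(−168/24) = 2^(−7) = 0.78%; 2^(−168/20) = 2^(−8.4) = 0.30%.
- Early leavers, departure time assumed. At 24 h: 2^(−1) = 50% and 2^(−1.2) = 44%. At 72 h: 2^(−3) = 12.5% and 2^(−3.6) = 8.2%.

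For completers, late drug-caused events are therefore unlikely to be numerous. That reassurance does not extend to a subject who leaves early, possibly because of an AE.

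**The case against.** The strongest reply is that the definitions are called guidelines and the reasonable-possibility sentence comes straight after them, so an Investigator could use it as the tie-break. The Study Manual and the case report form guidance are not visible and may settle the matter. Healthy, confined subjects with few concomitant drugs also make competing causes less common, as Protocol Section 3.2 notes. The safety analysis is purely descriptive, and all AEs collected are listed whatever their code.

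Much of this stands. Inconsistent coding is possible but not demonstrated, and the affected events are probably few and mostly mild. Discomfort from blood draws, or acetaminophen at no more than 2 g/day, is not a convincing cause of a clinically significant Grade 3 event, which further limits the effect on rules 3a and 3b.

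It does not remove the point. A tie-break that the text assigns to a different term is not a rule. Listing every recorded AE also does not help after EOT or ET, where an event judged NOT RELATED may leave no AE record at all. Restrictions on medication, alcohol and caffeine end at EOT or ET (Protocol 6.1, 6.2), so competing causes become more available just as the filter begins.

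It can also be said that reasonable possibility is itself a matter of judgement. That is true. The proposed wording makes the two codes exhaustive and exclusive; it does not make assessors agree.

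**Conclusion.** The defect is real but narrow. The two definitions leave 2 of 6 timing-by-cause cells without a code, and one of these, consistent timing with an identified other cause, matters in practice. The main effects are on which non-serious AEs are recorded between EOT/ET and EOS, and on the treatment-related TEAE tables. How many events would be affected cannot be estimated from the documents. The conclusion rests on the literal wording of the protocol and SAP alone.

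A reader might infer three stronger things that the documents do not support:

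- **That dose escalation is unsafe because rules 3a and 3b can be bypassed.** The code changes a formal trigger, but escalation review covers all AEs and the available actions do not depend on it.
- **That serious-event reporting is compromised.** The FDA-reportable definition does use related, but every SAE is notified within 24 hours whatever its code, and the Sponsor makes the final decision on suspected unexpected serious adverse reactions.
- **That any competing cause disqualifies RELATED, or that a third of events are uncodable.** An event with consistent timing and a cause that is only suspected still meets RELATED, and 2 of 6 counts logical cells, not events.

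**What to change.** In Appendix 1, replace the two definitions with:

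- RELATED: there is a reasonable possibility that the drug caused the event, even if another cause is also possible.
- NOT RELATED: there is no such reasonable possibility.

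State in Section 5.5 that *drug-related* uses this definition, since that section does not now refer to Appendix 1. Section 7.2.1 and SAP Section 8.6.1 use the Investigator's code and need no edit. Case report form guidance needs the same change if it repeats the current text.

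Apply one definition to all cohorts. Cohorts are dosed in sequence, so a broader definition introduced partway would coincide with higher doses and could look like a dose trend in related events. SAP Section 10 says the levels are confirmed as 300, 600, 800 and 900 mg, so some or all cohorts may already be coded. In that case keep the codes first assigned and state in the clinical study report which definition applied to each cohort. Any re-assessment should be done before database lock and shown beside those codes, because re-judging causality in an open-label study carries its own bias.

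The cost is a protocol amendment that plausibly needs written Sponsor, Investigator and IRB approval under Protocol Section 9.1, and somewhat more events labelled related.
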